### 4.3. Premature Withdrawal from the Study

A patient has the right to withdraw from the study at any time, for any reason, and without repercussion. The parent/caregiver has the right to withdraw permission to have the patient participate in the study at any time, for any reason, and without repercussion.

The investigator and sponsor have the right to withdraw a patient from the study in the event of an intercurrent illness, AE, treatment failure, protocol violation, cure, and for administrative, or other reasons. An excessive rate of withdrawals would render the study uninterpretable; therefore, unnecessary withdrawal of patients should be avoided.

Patients who withdraw prematurely from the study will be asked to complete study assessments per section 6.1.

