During the treatment period, patients will have weekly in-clinic visits through week 4, and then in-clinic visits every 4 weeks through week 16 with weekly telephone visits in between the in-clinic visits. Patients and/or parents/caregivers (as deemed appropriate based on age of patient) will be trained on injecting study drug during in-clinic visit 2 (day 1) to visit 6 (week 4). During weeks in which no in-clinic visit is scheduled, patients will either self-inject study drug or the parent/caregiver will administer study drug to the patient. In case patients do not want to self-inject and the parent/caregiver do not want to administer study drug to patient, patients may have the clinic staff administer all the study drug injections in the clinic. Safety, laboratory, and clinical assessments will be performed at specified clinic visits, as noted in [Table 1](#). The end of treatment period visit will occur at week 16, two weeks after the last dose of study drug. The co-primary endpoints will be assessed at this visit. If patients prematurely discontinue study treatment, the patients will be encouraged to stay in the study to have data collected at all remaining scheduled visits until completion of the planned end of study visit.

Patients who participate in the study may subsequently be eligible to participate in an open-label extension study.

Patients who decline to enroll in the open-label extension study will be followed up for 12 weeks. For these patients, after week 16, follow-up visits will occur every 4 weeks from week 20 through week 28. During the follow-up period, patients will be monitored for safety and tolerability and have laboratory and clinical assessments per schedule as noted in [Table 2](#).

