## **5.3. Rescue Treatment**

If medically necessary (ie, to control intolerable AD symptoms), rescue treatment for AD may be provided to study patients at the discretion of the investigator. If possible, investigators are encouraged to consider rescue initially with topical treatment (eg, medium/high potency TCS) and to escalate to systemic medications only for patients who do not respond adequately after at least 7 days of topical treatment. Topical calcineurin inhibitors may be used for rescue, alone or in combination with TCS, but the use of TCIs should be reserved for problem areas only (eg, face, neck, intertriginous and genital areas, etc.). Investigators may also consider rescue with crisaborole. Rescue treatment for these topical therapies should be used as per prescribing information and local guidelines. Patients may continue study treatment if rescue consists of topical medications.

Patients who receive systemic corticosteroids or systemic nonsteroidal immunosuppressive drugs (eg, cyclosporine, methotrexate, mycophenolate-mofetil, azathioprine, etc) as rescue medication during the study will be discontinued permanently from the study drug. All patients will be asked to complete the scheduled study visits and assessments whether or not they complete study treatment and whether or not they receive rescue treatment for AD. Investigators should make every attempt to conduct efficacy and safety assessments (eg, disease severity scores, safety laboratory tests) immediately before administering any rescue treatment. An unscheduled visit may be used for this purpose, if necessary. For the purpose of efficacy analysis, patients who receive rescue treatment during the study will be considered treatment failures.

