#### 9.5.2.1. Primary Efficacy Analysis

The Cochran-Mantel-Haenszel test adjusted by randomization strata (baseline disease severity and weight group) will be used for analyzing the percentage of patients with IGA 0 or 1 at week 16 or percentage of patients with EASI-75 at week 16.

All efficacy data, regardless of the patient being on the study treatment or discontinues the study treatment but remains in the study, will be used for analysis. Specifically, if a patient stays in the study until the end of the study planned placebo-controlled treatment period, all efficacy data collected up to the study planned end of treatment visit will be included in the primary analysis, regardless if the patient is on treatment or not.

To account for the impact of rescue treatment on the efficacy effect: For the primary efficacy endpoints (which are binary efficacy endpoints), if rescue treatment is used (see section 5.3), the patient will be classified as a nonresponder from the time the rescue is used.

If a patient withdraws from study, this patient will be counted as a nonresponder for endpoints after withdrawal.

The Mantel-Fleiss (MF) criterion will be performed, and if it is not met while using the option CMH (MF) in SAS procedure PROC PREQ, sensitivity analyses including each factor separately in CMH test will be conducted. Sensitivity analysis using the last observation carried forward (LOCF) approach to determine patient's status at week 16 will be conducted to assess the robustness of the primary efficacy analysis with regards to handling of missing data. The efficacy data will be set to missing after rescue treatment is used, then the LOCF method will be used to determine patients' status at week 16.

In addition, the Cochran-Mantel-Haenszel method adjusted by randomization strata will also be performed on all observed data regardless if rescue treatment is used. A patient with missing data will be counted as a nonresponder. Other sensitivity analyses may be conducted.

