#### Handling of dropouts or adjudicated rescue treatment or missing value for the binary response variables as the primary analysis

- If a patient withdraws from the study, this patient will be counted as a non-responder for the time points after withdrawal.
- To account for the impact of rescue treatment on the efficacy effect: if rescue treatment is used (see Section 4.3 for rescue treatment), the patient will be specified as a non-responder from the time the rescue treatment is used.
- If the patient has the missing value at week 16, then it will be counted as a non-responder at week 16.

The Mantel-Fleiss (MF) criterion will be performed, and if it is not met while using the option CMH (MF) in SAS procedure PROC PREQ, sensitivity analyses including each factor separately in CMH test will be conducted.

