### Sensitivity analyses

1. Post-baseline Last Observation Carried Forward (LOCF) approach after censoring for rescue treatment use or study withdrawal to determine patient's status at week 16 will be conducted to assess the robustness of the primary efficacy analysis with regards to handling of missing data.
2. All observed data, regardless if rescue treatment is used or data is collected after withdrawal from study treatment will be included for analysis. Patients with missing value will be counted as non-responder.

The primary efficacy analyses will be performed on FAS, as well as on PPS as a supporting analysis.

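### Protocol 4.3 permits removal from the study for treatment failure, protocol violation or cure, which conflicts with the plan's retention rules and can score a cured patient as a nonresponder

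*Protocol*

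**What the plan says.** Protocol 4.3 first sets out the right of the patient and the parent to withdraw. It then gives the investigator and sponsor the right to "withdraw a patient from the study in the event of an intercurrent illness, AE, treatment failure, protocol violation, cure", with administrative and other reasons added. The same paragraph warns that too many withdrawals would make the study impossible to interpret, and says that "unnecessary withdrawal of patients should be avoided". It ends by asking patients who leave early to complete the assessments in section 6.1, which include an early termination visit.

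Elsewhere the plan separates stopping study drug from leaving the study:

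- Protocol 3.1: "If patients prematurely discontinue study treatment, the patients will be encouraged to stay in the study".
- Protocol 5.3: "All patients will be asked to complete the scheduled study visits and assessments whether or not they complete study treatment". The sentence goes on to cover rescued patients as well.
- Protocol 5.4.2 asks patients who permanently stop study drug but remain in the study to return for every remaining visit.

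The scoring rules make no distinction by reason for withdrawal. Protocol 9.5.2.1: "If a patient withdraws from study, this patient will be counted as a nonresponder for endpoints after withdrawal". SAP 5.7.1: "If a patient withdraws from the study, this patient will be counted as a non-responder for the time points after withdrawal". SAP 5.7.1 has two sensitivity analyses for the binary endpoints. The first is LOCF, an "approach after censoring for rescue treatment use or study withdrawal to determine" week-16 status. The second uses all observed data, and there "Patients with missing value will be counted as non-responder".

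For continuous endpoints, SAP 5.7.2 sets values after rescue to missing and then applies multiple imputation (MI).

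**The concern.** Two of the three grounds, treatment failure and cure, are judgments about the efficacy outcome. If a site acts on them, whether week-16 data exist depends on how the patient is doing. The third, protocol violation, is not an outcome, but it ends follow-up on a randomized patient whom the as-randomized analysis must still count.

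The clearest harm is in the primary endpoint. A site that releases a clear patient as cured at week 12 is within 4.3, yet the analysis then records a week-16 failure. For treatment failure, the harm is lost week-16 EASI and pruritus values, and lost data for the sensitivity analyses meant to show results whether or not rescue was used.

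Protocol 5.3 also counts rescued patients as treatment failures for efficacy analysis while asking them to stay. A site could read 4.3 as permission to remove the patients that 5.3 wants kept.

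**Working it through.** **1. Removal as cured, before week 16.** SAP 6.4 maps early termination visits by study day: week 12 is days 72 to 99 and week 16 is days 100 to 127. An early termination visit at day 85 therefore supplies a week-12 value, not a week-16 value.

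- Primary analysis: nonresponder.
- All-observed sensitivity analysis: week 16 is missing, so nonresponder.
- LOCF sensitivity analysis: responder, if the last observed status was a response and no rescue was used.

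If the early termination visit falls on days 100 to 112, SAP 6.4 could supply a week-16 value, but SAP 5.7.1 makes time points after withdrawal nonresponse. The SAP does not say which rule prevails.

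**2. Removal for treatment failure.**

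- Binary endpoints: nonresponse is usually the right value.
- Primary continuous analysis, rescued patients: no week-16 value is lost, because data after rescue are set to missing anyway.
- Primary continuous analysis, unrescued patients: week-16 EASI and pruritus values are lost and imputed.
- All-observed sensitivity analyses: these lose the observations after rescue that they are designed to use.

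The MI model in SAP 5.7.2 includes treatment, strata, baseline and the endpoint at each clinic visit, so it uses the patient's own earlier values. Withdrawal driven by recorded scores can still be missing at random. The concern is withdrawal driven by judgment that no recorded score reflects.

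**3. Removal for protocol violation.** The FAS is all randomized patients (Protocol 9.3.1), so the patient stays in it but contributes no further data.

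**4. Size of the cure misscoring.** Inputs from Protocol 9.2: 80 patients per group, two-sided 5%, IGA 0/1 rates of 37% (Q2W), 29% (Q4W) and 9% (placebo), stated power 98% and 88%.

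*Reproducing the stated power.* The documents name no method. Exact power of Fisher's two-sided test gives 98.9% and 88.1% for IGA. For all six stated powers it gives 98.9, 88.1, 99.8, 99.4, 97.7 and 95.9, against 98, 88, 99, 99, 97 and 95. The pooled normal formula gives 99.1% and 90.5% for IGA. It is used below to show changes, so its starting point for Q4W is 2.5 points above the stated figure.

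*One patient.* 1/80 = 1.25 points. Two in the Q4W arm: 0.29 × 80 = 23.2 responders; (23.2 − 2)/80 = 26.5%, a loss of 2.5 points, or one eighth of the assumed 20-point difference.

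*A range.* The documents give no rate, so let c be an assumed share of would-be week-16 responders removed as cured. Each affected rate becomes p(1 − c). With p̄ the mean of the two rates and n = 80:

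power = Φ{ [ |p1 − p2| − 1.96 √(2p̄(1 − p̄)/n) ] / √( [p1(1 − p1) + p2(1 − p2)]/n ) }

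At c = 10% in every arm, the patients misscored are 0.10 × 29.6 = 2.96 (Q2W), 0.10 × 23.2 = 2.32 (Q4W) and 0.10 × 7.2 = 0.72 (placebo).

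| c | Arms affected | Q2W difference, power | Q4W difference, power |
|---|---|---|---|
| 0 | none | 28.0 points, 99.1% | 20.0 points, 90.5% |
| 5% | all | 26.6, 98.7% | 19.0, 88.5% |
| 10% | all | 25.2, 98.1% | 18.0, 86.3% |
| 20% | all | 22.4, 96.2% | 16.0, 81.1% |
| 10% | active only | 24.3, 97.1% | 17.1, 81.8% |
| 20% | active only | 20.6, 91.8% | 14.2, 68.9% |
| 10% | placebo only | 28.9, 99.5% | 20.9, 93.3% |

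The difference grows only in the placebo-only row. Q4W on IGA has the lowest stated power and is step 10 of the fixed sequence in SAP 5.7.2; failing it stops formal testing of steps 11 to 40.

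**The case against.** The other side has real force.

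- **The right is discretionary.** It sits beside a caution against its use, and Protocol 3.1, 5.3 and 5.4.2 all point to retention. A reader might infer that 4.3 cancels the retention design. The documents do not support that: they contain a conflict, with no sign of how often a site would act on it.
- **Cure within 16 weeks looks unlikely.** Protocol 1.1 describes a long-term, relapsing disease, and entry requires at least a year since diagnosis, IGA of 3 or more and EASI of 16 or more. Protocol 5.8 also gives no earlier access to the open-label extension for leaving early.
- **Status at withdrawal is meant to be recorded.** The early termination visit includes IGA, EASI and pruritus, so it would be wrong to infer that every early leaver lacks a usable week-16 value. Before day 100, however, that visit does not supply one for IGA or EASI.
- **Imputation is not simply from patients who stayed.** It also uses the patient's own earlier values, and LOCF and worst-observation analyses are planned for EASI and/or pruritus.
- **The prespecified rule is conservative if cure is commoner on active drug.** A reader might infer a risk of a false positive claim. With equal shares in every arm, or more on active drug, the error runs against dupilumab.
- **Withdrawals would be visible.** SAP 5.4 tabulates study discontinuations by reason.

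These points limit the size. They do not remove the contradiction, or the wrong primary-endpoint value when a responder is removed as cured before the week-16 window.

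**Conclusion.** The concern holds as a conflict in the protocol with a small but avoidable cost. Protocol 4.3 permits removals that 3.1, 5.3 and 5.4.2 are written to prevent. For a responder removed as cured before day 100, the primary and all-observed analyses return the wrong value and only LOCF does not. For treatment failure, the loss is limited to week-16 continuous values in unrescued patients and to the all-observed analyses. For protocol violation, it is follow-up data only; a reader might infer outcome-dependent missingness or exclusion from the FAS there too, and the documents support neither.

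The size is 1.25 points per misscored responder in an 80-patient arm. At an assumed 10% of responders in every arm, power falls by about 1 point (Q2W) and 4 points (Q4W). These figures rest on the plan's assumed response rates and on a cure-withdrawal share that the documents do not give. This is a cheap improvement to make, not a threat to the validity of a positive result.

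**What to change.** Reconcile Protocol 4.3 with 3.1, 5.3 and 5.4.2:

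- Delete treatment failure, protocol violation and cure as grounds on which the investigator or sponsor may withdraw a patient from the study.
- State that the residual category of other reasons does not include them; otherwise the deletion prevents nothing.
- State that such patients, on or off study drug, are asked to attend the remaining visits, at least week 16.

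Leave unchanged the withdrawal rights of patient and parent, the intercurrent illness, AE and administrative grounds, and every rule on stopping study drug. The argument here gives no reason to narrow those.

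The cost is one paragraph of protocol wording, a note to sites, and a few extra scheduled visits for patients who would otherwise have been released.

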### 4.4. Replacement of Patients

Patients prematurely discontinued from the study or study treatment will not be replaced.

## 5. STUDY TREATMENTS

### 5.1. Investigational and Reference Treatments

Dupilumab 175 mg/mL: Each 1.14 mL single-use, prefilled glass syringe with snap-off cap delivers 200 mg of study drug (1.14 mL of a 175 mg/mL solution).

Dupilumab 150 mg/mL: Each 2.25 mL single-use, prefilled glass syringe with snap-off cap delivers 300 mg of study drug (2.0 mL of a 150 mg/mL solution)

Placebo matching dupilumab is prepared in the same formulation without the addition of protein (ie, active substance, anti-IL-4R $\alpha$  monoclonal antibody).

Patients will be randomized to receive 1 of the following treatment regimens:

- Dupilumab Q2W treatment:
  - Patients <60 kg in baseline body weight: SC injections of dupilumab, 400 mg loading dose on day 1, then 200 mg Q2W from week 2 to week 14, or
  - Patients  $\geq$ 60 kg in baseline body weight: SC injections of dupilumab, 600 mg loading dose on day 1, then 300 mg Q2W from week 2 to week 14
- Dupilumab Q4W treatment: SC injections of dupilumab, 600 mg loading dose on day 1, then 300 mg Q4W from week 4 to week 12; in order to maintain the blind, there will be an SC injection of placebo in between dupilumab doses during the week 2 to week 14 dosing period so the injection frequency will match the other 2 groups.
- Placebo: SC injections of placebo matching dupilumab Q2W (including doubling the amount of placebo on day 1 to match the loading dose). In order to maintain blinding for the study, patients in the <60 kg weight stratum who are randomized to the placebo group will receive, in a 1:1 ratio, either placebo matching 200 mg dupilumab (including doubling the amount of placebo on day 1 to match the loading dose) or placebo matching 300 mg dupilumab (including doubling the amount of placebo on day 1 to match the loading dose). In the  $\geq$ 60 kg weight stratum, the patients randomized to the placebo group will receive placebo matching 300 mg dupilumab.

In order to maintain blinding, all patients will receive an injection Q2W from day 1 to week 14. Patients will receive placebo injection at the weeks dupilumab is not given.

Study drug will be administered per the scheduled described in section 6.1.

Subcutaneous injection sites of the study drug should be alternated among the different quadrants of the abdomen (avoiding navel and waist areas), upper thighs, and upper arms so that the same site is not injected for 2 consecutive weeks. To allow for adequate assessment of possible injection site reactions, study drug should be administered only into areas of normal-looking skin. Instructions for recording and reporting injection site reactions will be provided in the study reference manual.

Patients will have the option to administer study drug (or have a caregiver administer study drug) outside the study site during weeks in which no in-clinic visit is scheduled. The study staff will train the patient/caregiver on preparation and administration of study drug on day 1 and will administer the first of the 2 injections required for the loading dose. The patient/caregiver will administer the second injection required for the loading dose under the supervision of the clinic staff. The patient/caregiver will administer study drug under the supervision of the clinic staff at visits 4 and 6 (weeks 2 and 4, respectively) and at other in-clinic visits. Patients will be monitored at the study site for a minimum of 30 minutes after the first 3 doses of study drug (visits 2 [day 1], 4 [week 2], and 6 [week 4]); vital signs (sitting blood pressure, heart rate, and respiratory rate) and AE assessments will be done at 30 minutes ( $\pm$ 10 minutes) post dose. The

patient (or caregiver) will administer study drug outside of the clinic during weeks in which no clinic visit is scheduled.

Patients (or caregivers) who prefer to have the clinic staff administer study drug may choose to have injections administered in the clinic.

## **5.2. Background Treatment**

All patients are required to apply moisturizers (emollients) at least twice daily for at least the 7 consecutive days immediately before randomization. After randomization, patients are required to continue to apply moisturizers throughout the study (all 28 weeks where applicable). However, to allow adequate assessment of skin dryness, moisturizers should not be applied for at least 8 hours before each clinic visit. All types of moisturizers are permitted, but patients may not initiate treatment with prescription moisturizers or moisturizers containing additives during the screening period or during the study. Patients may continue using stable doses of such moisturizers if initiated before the screening visit.

## **5.3. Rescue Treatment**

If medically necessary (ie, to control intolerable AD symptoms), rescue treatment for AD may be provided to study patients at the discretion of the investigator. If possible, investigators are encouraged to consider rescue initially with topical treatment (eg, medium/high potency TCS) and to escalate to systemic medications only for patients who do not respond adequately after at least 7 days of topical treatment. Topical calcineurin inhibitors may be used for rescue, alone or in combination with TCS, but the use of TCIs should be reserved for problem areas only (eg, face, neck, intertriginous and genital areas, etc.). Investigators may also consider rescue with crisaborole. Rescue treatment for these topical therapies should be used as per prescribing information and local guidelines. Patients may continue study treatment if rescue consists of topical medications.

Patients who receive systemic corticosteroids or systemic nonsteroidal immunosuppressive drugs (eg, cyclosporine, methotrexate, mycophenolate-mofetil, azathioprine, etc) as rescue medication during the study will be discontinued permanently from the study drug. All patients will be asked to complete the scheduled study visits and assessments whether or not they complete study treatment and whether or not they receive rescue treatment for AD. Investigators should make every attempt to conduct efficacy and safety assessments (eg, disease severity scores, safety laboratory tests) immediately before administering any rescue treatment. An unscheduled visit may be used for this purpose, if necessary. For the purpose of efficacy analysis, patients who receive rescue treatment during the study will be considered treatment failures.

